4.1.2 Radiation Therapy Prescription Dose

The treating radiation oncologist can choose to deliver 10 or 12 Gy per fraction depending on the clinical circumstances, i.e. anatomical location and adjacent organs-at-risk. Each radiation therapy fraction will encompass the 95% of the planning target volume, and is considered compliant to the protocol. The following table lists the acceptable range of dose per fraction, with preference for the higher dose if safely achievable. Any dose delivered that is beyond the recommended doses will be considered an unacceptable variation.

Number of fractions	Dose per fraction	Total dose
3	10-12 Gy	30-36 Gy

4.1.3 Prescription Interval

Each PULSAR fraction may be delivered every 2 weeks to potentiate the synergy between ICI and radiotherapy, until the completion of the prescribed number of fractions. PULSAR may be held if the patient does not have any targetable disease. Each PULSAR treatment and date of treatment delivery will be recorded.

4.1.4 Radiation Treatment Concerns and Concurrent Medications

Analgesic premedication to avoid general discomfort during long treatment durations is recommended when appropriate.

4.2 Technical Factors and Considerations

4.2.1 Physical Factors

Only photon (x-ray) beams produced by linear accelerators with photon energies of 4-15 MV will be allowed. Cobalt-60 and charged particle beams (including electrons, protons, and heavier ions) are not allowed. Restriction of photon beam energies > 10 MV but less than 15 MV will be based on clinical appropriateness taking into account distance the beam must travel to the target.

4.2.2 Dose Verification at Treatment

In-vivo dosimeter measurements (e.g., diode, TLD) may be obtained for surface dose verification for accessible beams. This information is not required by the protocol.

4.2.3 Treatment Platforms

The trial allows most commercially available photon or proton producing treatment units. Treatment units should include image guidance. Both 3D conformal and intensity-modulated radiation therapy (including volumetric-modulated arc therapy (VMAT)) are allowed. Proton or other charged particle units are not allowed in this study. Other specialized accelerators (e.g., the CyberKnife® or Tomotherapy) are allowed as long as they meet the technical specifications of the protocol.

4.3 Simulation and Image Guidance

4.3.1 Patient Positioning

Patients will be positioned in a stable position that allows accurate reproducibility of the target between treatments. Positions uncomfortable for the patient should be avoided so as to prevent uncontrolled movement during treatments. A variety of immobilization systems may be utilized including stereotactic frames that surround the patient on three sides and large rigid pillows (conforming to patients external contours) with reference to the stereotactic coordinate system. Patient immobilization must be reliable enough to ensure that the Gross Tumor Volume (GTV) does not deviate beyond the confines of the Planning Treatment Volume (PTV) with any significant probability (i.e. < 5%).

4.3.2 Image Guidance

Isocenter or reference point port localization images should be obtained on the treatment unit immediately before treatment to ensure proper alignment of the geometric center (i.e. isocenter) of the simulated fields. These IGRT images can be obtained with planar kV imaging devices or cone-beam CT equipment. For treatment systems that use kV imaging but also allow EPID imaging using the treatment beam, orthogonal images verifying the isocenter also should be obtained.

4.4 Treatment Planning and Target Volumes

4.4.1 Image Acquisition

Computed tomography will be the primary image platform for targeting and treatment planning. The planning CT scans must allow simultaneous view of the

patient anatomy and fiducial system for stereotactic targeting. CT scan with IV contrast is recommended unless the patient has allergy to contrast or renal insufficiency. Axial acquisitions will be required with spacing ≤ 3.0 mm between scans. Images will be transferred to the treatment planning computers.

4.4.2 Target Volumes

The target lesion will be outlined by an appropriately trained physician and designated the gross tumor volume at the primary site (GTVp) and nodal site(s) GTVn. The targets will generally be drawn using appropriate windowing based on location of the primary tumor and metastatic lymph nodes. Given that this treatment will adapt to changes in tumor dimension, the clinical target volume (CTV) will correspond to the GTVp/GTVn with no added margin. A 5 mm planning target volume (PTV) margin will be added to account for setup and internal motion.

4.5 Dosimetry

4.5.1 Intensity Modulated Radiation Therapy (IMRT)

IMRT, including volumetric-modulated arc therapy (VMAT) and modulated charged particles is allowed in this study. The number of segments (control points) and the area of each segment should be optimized to ensure deliverability and avoid complex beam fluences. Ideally, the number of segments should be minimized, and the area of each segment should be maximized (the aperture of one segment from each beam should correspond to the projection of the PTV along a beam's eye view).

4.5.2 Dose Calculations

For purposes of dose planning and calculation of monitor units for actual treatment, this protocol will require tissue density heterogeneity correction.

Successful treatment planning will require accomplishment of all of the following criteria:

1. Maximum dose: The treatment plan should be created such that 100% corresponds to the maximum dose delivered to the patient. This point must exist within the PTV.
2. Prescription isodose: The prescription isodose surface must be $\geq 60\%$ and $< 90\%$ of the maximum dose.
3. Prescription Isodose Surface Coverage: The prescription isodose surface will be chosen such that 95% of the target volume (PTV) is conformally covered by the prescription isodose surface (PTV V95%RX = 100%) and 99% of the target volume (PTV) receives a minimum of 90% of the prescription dose (PTV V90%RX $> 99\%$).

4.6 Normal Tissue Dose Constraints

4.6.1 The following table lists the specific organ and dose fractionation constraints on normal tissue. Given the irregular, long intervals between each radiotherapy fraction, total dose will be calculated to a particular organ-at-risk to ensure safety of radiation therapy. Exceeding these dose tolerances by more than 2.5%

constitutes a minor protocol violation. Exceeding these dose tolerances by more than 5% constitutes a major protocol violation.

Three Fraction

Serial Tissue	Volume	Volume Max (Gy)	Max Point Dose (Gy)**	Endpoint (\geq Grade 3)
Optic Pathway	<0.2 cc	15.3 Gy	17.4 Gy	neuritis
Cochlea			14.4 Gy	hearing loss
Brainstem (not medulla)	<0.5 cc	15.9 Gy	23.1 Gy	cranial neuropathy
Spinal Cord and medulla	<0.35 cc	15.9 Gy	22.5 Gy	myelitis
Cauda Equina	<5 cc	21.9 Gy	25.5 Gy	neuritis
Sacral Plexus	<5 cc	22.5 Gy	25.5 Gy	neuropathy
Esophagus*	<5 cc	27.9 Gy	32.4 Gy	esophagitis
Brachial Plexus	<3 cc	22 Gy	26 Gy	neuropathy
Heart/Pericardium	<15 cc	24 Gy	30 Gy	pericarditis
Great vessels	<10 cc	39 Gy	45 Gy	aneurysm
Trachea and Large Bronchus*	<5 cc	39 Gy	43 Gy	impairment of pulmonary toilet
Bronchus- smaller airways	<0.5 cc	25.8 Gy	30 Gy	stenosis with atelectasis
Rib	<5 cc	40 Gy	50 Gy	Pain or fracture
Skin	<10 cc	31 Gy	33 Gy	ulceration
Stomach	<5 cc	22.5 Gy	30 Gy	ulceration/fistula
Bile duct			36 Gy	stenosis
Duodenum*	<5 cc	22.5 Gy	30 Gy	ulceration
Jejunum/Ileum*	<30 cc	20.7 Gy	28.5 Gy	enteritis/obstruction
Colon*	<20 cc	28.8 Gy	45 Gy	colitis/fistula
Rectum*	<3.5 cc	43 Gy	47 Gy	proctitis/fistula
	<20 cc	30.3 Gy		
Ureter			40 Gy	stenosis
Bladder wall	<15 cc	17 Gy	33 Gy	cystitis/fistula
Penile bulb	<3 cc	25 Gy		impotence
Femoral Heads	<10 cc	24 Gy		necrosis
Renal hilum/vascular trunk	15 cc	19.5 Gy		malignant hypertension
Parallel Tissue	Critical Volume (cc)	Critical Volume Dose Max (Gy)		Endpoint (\geq Grade 3)
Lung (Right & Left)	1500 cc for males and 950cc for females***	10.8 Gy		Basic Lung Function
Lung (Right & Left)			V-11.4Gy<37%	Pneumonitis
Liver	700 cc***	17.7 Gy		Basic Liver Function
Renal cortex (Right & Left)	200 cc***	14.7 Gy		Basic renal function

*Avoid circumferential irradiation

** “point” defined as 0.035cc or less

***or one third of the “native” total organ volume (prior to any resection or volume reducing disease), whichever is greater

4.8 Concomitant Medications/Treatments

Any ICI agent approved for use in advanced urothelial carcinoma may be used in this study. Currently approved agents for use in the second line setting (i.e., after chemotherapy or Cohort 2) include atezolizumab, avelumab, duvalumab, nivolumab, and pembrolizumab. Approved agents for use in the first line setting (i.e., in chemotherapy-ineligible or Cohort 1) include atezolizumab and pembrolizumab. Patients are eligible if they are planned to initiate ICI, or if they are within 1-3 weeks of initiation of an approved ICI agent. Subjects should receive at least two, and may receive up to four, doses of ICI concurrent with PULSAR prior to undergoing surgery. PULSAR will be initiated no less than one week after receipt of the first dose of ICI.

This use of ICI is considered a standard of care therapy. The drug will be administered and managed by the treating medical oncologist. Continuation beyond the study period per standard of care is at the discretion of the treating medical oncologist. If additional immune checkpoint inhibitor (anti-PD1, anti-PD-L1, and/or anti-CTLA4) agents are approved for use in advanced urothelial carcinoma during the study, these agents will be permitted as well. If FDA approval is withdrawn or if agents are voluntarily withdrawn by the manufacturers for the relevant clinical indications, the agents will not be permitted for new study enrollments. Patients already on such agents will be permitted to remain in the study. Switching from one approved agent to another while on the study is permitted at the treating clinician's discretion.

4.9 Other Modalities or Procedures

No other modalities of treatment are planned. Patients are expected to receive any and all indicated interventions according to the usual standard of care.

4.10 Duration of Therapy

The trial therapy will be considered complete when patients finish the third of three fractions of PULSAR. "In the absence of treatment delays due to adverse events, treatment may continue until that point or until:

- Disease progression
- Inter-current illness that prevents further administration of treatment
- Unacceptable adverse event(s)
- Subject decides to withdraw from the study, **OR**
- General or specific changes in the patient's condition render the subject unacceptable for further treatment in the judgment of the investigator.

4.11 Duration of Follow Up

All follow up after radical cystectomy represents the standard of care. Patients will be followed for adverse outcomes for 90 days following radical cystectomy. After that point, subjects will only be followed for progression-free and overall survival for two years from the date of first PULSAR treatment or disease recurrence, whichever occurs first.

4.12 Removal of Subjects from Protocol Therapy

Subjects will be removed from therapy when any of the criteria listed in Section 5.5 apply. Notify the Principal Investigator, and document the reason for treatment discontinuation and the date of discontinuation. The subject should be followed-up per protocol.

4.13 Subject Replacement

Any subjects removed from the study that have not completed at least one fraction of radiation should be replaced by additional recruitment of study subjects.

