2.3 Primary Endpoints

2.3.1 The primary endpoint of the study is feasibility of RC after ICI + PULSAR, defined as the proportion of enrolled patients who complete three courses of PULSAR followed by radical cystectomy while remaining on ICI therapy, within sixteen weeks of initiation of PULSAR. It is anticipated that reasons for protocol non-completion may include progression to nonresectable disease and patient intolerance of treatment.

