3.0 SUBJECT ELIGIBILITY Subject Eligibility

Eligibility waivers are not recommended; however, if warranted, prior approvals are required per Section 11.6.1. Subjects must meet all inclusion and exclusion criteria to be registered to the study. Study treatment may not begin until a subject is registered. Once registered, a subject is still required to meet all inclusion and exclusion criteria on the first day of treatment, prior to treatment.

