4.0 TREATMENT PLAN

4.1 PULSAR: Dose and Techniques

Patients are eligible for the trial if they have bulky, clinically node-positive (cN+) bladder cancer and have either recently initiated (within \leq 1 week) or are planned to initiate immune checkpoint inhibitor (ICI) therapy due to either 1) ineligibility for/refusal of platinum-based downstaging chemotherapy; or 2) failure to achieve a complete clinical response to platinum-based downstaging chemotherapy. Patients will initiate PULSAR treatment 1-2 weeks after initiating ICI. PULSAR will be administered in 3 fractions of 12 Gy each (36 Gy total) at 12-16 day intervals and patients will undergo radical cystectomy with bilateral extended pelvic lymph node dissection within 4-8 weeks after completion of PULSAR. ICI therapy will be administered according to the FDA-approved dosing route and schedule and will be continued during PULSAR treatments.

PULSAR treatment will be initiated 1-2 weeks after the patient is initiated on an FDA-approved ICI agent. PULSAR will be administered in 3 fractions of 12 Gy each at 12-16 day intervals. Target areas will include the region of the bladder containing the primary tumor (confirmed, if necessary, on office flexible cystoscopy at UTSW) and to up to five targetable, pathologically enlarged bulky lymph nodes (as deemed feasible by the treating radiation oncologist). Non-enlarged pelvic lymph nodes will be spared to minimize adverse effects on the tumor immune response.

4.1.1 PULSAR will be delivered with the targeting, planning, and directing of treatment fields guided to a target based on known 3D coordinates related to reliable fiducial markers. This differs from conventional radiation therapy in which treatment is guided by skin or bony landmarks assumed to correlate to the target volume based on the initial simulation. Treatment will account for inter/intra-fractional errors with careful dosimetry that delivers an ablative dose to the involved lesions while respecting normal tissue constraints. In the event that fiducial placement is deemed unfeasible or unsafe, or would result in an unacceptable delay in treatment, fiducial placement may be omitted and targeting based on a combination of pre-treatment imaging and findings on flexible cystoscopy.

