9.2 Sample Size and Accrual

For the primary endpoint of feasibility, we define a target rate of protocol completion (completion of radical cystectomy within sixteen weeks of initiation of PULSAR) of 90%, with a lower boundary of futility at 60%. A sample size of 24 patients provides 91% power to reject a 60% completion rate at a two-sided alpha of 0.05. Of note, this sample size was employed in the recent NABUCCO trial, which addressed a similar high-risk patient cohort³⁶. Allowing a 10% drop out rate increases the desired enrollment to a total of **27 patients**. Given the desired enrollment of 27 patients and the three-year trial period, this will require accrual of nine patients per year across all sites.

For the secondary endpoint of progression-free survival, the trial-eligible subset of our recently published historic series of cN+ bladder cancer patients achieved a 2-year recurrence-free survival rate of 30%¹⁵. A sample size of 24 patients provides 90% power to detect a 27% absolute increase in 2-year recurrence free survival with a one-sided alpha of 0.10 using the Kaplan-Meier log-rank test.

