9.3 Data Analyses

The primary endpoint, protocol completion, will be assessed by calculating the proportion of patients completing radical cystectomy within sixteen weeks of initiating PULSAR treatment. If the proportion of patients undergoing cystectomy exceeds 60%, the null hypothesis (that use of ICI+PULSAR+RC is not feasible) will be deemed to have been rejected.

For the secondary endpoint, progression-free survival will be determined as described above, and will be reported by means of Kaplan-Meier survival curves, median progression-free survival time, and proportion of patients without progression at two years. Comparison will be made to the trial-eligible subset of patients in a historic control series using the log-rank test. The 2-year progression-free survival rate in the historic cohort was 30%. The null hypothesis will be rejected if the one-sided *p* value for the comparison is less than 0.10.

Additional planned analyses include the following, all of which will be reported with simple descriptive statistics (*n* / *N* and percentage):

Major complication rate: A major surgical complication will be defined as any postoperative complication of Clavien-Dindo Grade III or higher.

Pathologic outcomes: Pathologic outcomes will be defined as follows, based on the final surgical pathology report:

1. Pathologic complete response: no viable disease remaining in the specimen (ypT0 N0).
2. Pathologic non-muscle-invasive downstaging: primary tumor without muscle invasion, and no viable disease in lymph nodes (\leq ypT1 N0).
3. Pathologic organ-confined downstaging: primary tumor confined to detrusor muscle, and no viable disease in lymph nodes (\leq ypT2 N0).
4. Nodal complete response: no viable disease in lymph nodes, regardless of primary tumor stage (ypTany N0).

Residual disease: Residual disease at surgery will be defined as follows:

1. Microscopic residual disease (R1) will be defined as any positive soft tissue margin on the final surgical pathology report, excluding carcinoma *in situ* at ureteral margins.
2. Gross residual disease (R2) will be defined as any grossly positive tissue margin reported on a pathology report, *or* the operating surgeon's subjective report of grossly unresectable disease including bulky matted lymph nodes.

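### The primary denominator is unsettled: 2.3.1 counts enrolled patients, 4.13 replaces anyone removed before a first fraction, and 9.2 and 9.3 do not say how those patients are analysed

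*Combined protocol and SAP*

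**What the plan says.** Section 2.3.1 gives the primary endpoint, feasibility, as "defined as the proportion of enrolled patients who complete three courses of PULSAR followed by radical cystectomy while remaining on ICI therapy". The time limit is sixteen weeks from the start of PULSAR. The section adds that "reasons for protocol non-completion may include progression to nonresectable disease and patient intolerance of treatment".

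Section 4.13 states: "Any subjects removed from the study that have not completed at least one fraction of radiation should be replaced". It does not restrict the reason for removal. The reasons listed in 5.5 include progression, toxicity and withdrawal.

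Section 9.3 will assess the endpoint by "calculating the proportion of patients completing radical cystectomy within sixteen weeks of initiating PULSAR treatment". It does not define which patients these are, and it declares the null hypothesis rejected if the proportion exceeds 60%.

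Section 9.2 sizes the trial at 24 patients for 91% power against a 60% rate (target 90%, two-sided alpha 0.05) and continues: "Allowing a 10% drop out rate increases the desired enrollment to a total of" 27. It does not say whether a drop-out is a failure or is left out.

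Patients can be lost between enrolment and the first fraction. Section 3.1.7 allows enrolment before the checkpoint inhibitor has started, and under 4.1 "Patients will initiate PULSAR treatment 1-2 weeks after initiating ICI". Section 3.0 adds: "Once registered, a subject is still required to meet all inclusion and exclusion criteria on the first day of treatment".

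**The concern.** A patient who enrols and then progresses, becomes intolerant of treatment or withdraws before the first fraction is a non-completer under 2.3.1. Under 4.13 the same patient is replaced. Under 9.3 that patient has no date from which to count sixteen weeks. The plan therefore gives conflicting signals about the denominator of its only primary endpoint.

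If replaced patients are left out, the trial estimates completion among those who reached PULSAR while reporting against an endpoint defined for everyone enrolled. Any early losses then push the estimate upward. In a trial of 24 to 27 patients, one to three of them can decide the result. With the denominator open, it could also be chosen after the results are known.

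**Working it through.** **1. The rules side by side**

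| Section | Denominator implied | Patient lost before the first fraction |
|---|---|---|
| 2.3.1 | Enrolled patients | Non-completer, read literally |
| 4.13 | Not stated | Replaced, whatever the reason |
| 9.2 | 24, raised to 27 for drop-out | Not stated |
| 9.3 | Patients, undefined; clock starts at PULSAR | No start date for the clock |
| 6.2 (safety only) | At least one fraction received | Excluded |

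No section says that replaced patients leave the primary analysis, and none says that they are counted as failures.

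**2. The plan's own figures**

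Inputs from 9.2: n = 24, null rate 0.60, target 0.90, two-sided alpha 0.05, so an upper tail of at most 0.025. For an exact binomial test the smallest passing count is 20:

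- P(X ≥ 20 | 24, 0.60) = 0.0134
- P(X ≥ 20 | 24, 0.90) = 0.915, against the stated 91%
- 24 / (1 − 0.10) = 26.7, rounded up to 27, as stated

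The cut-off of 20/24 is derived here and does not appear in the plan. The rule written in 9.3 is a different one, an observed proportion above 60%. The two are kept apart below.

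**3. Effect on the 9.3 rule**

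The loss rate before PULSAR is not given. Assume three early losses, each replaced, so that 27 are treated and 30 enrolled. With 17 completers:

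- replaced patients left out: 17/27 = 63.0%, passes
- replaced patients kept as failures: 17/30 = 56.7%, fails

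The 9.3 rule has a separate weakness: at n = 27 it passes at 17, and P(X ≥ 17 | 27, 0.60) = 0.458 even with no replacement. The exact test is therefore the better gauge.

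**4. Effect on the exact test, with 24 starters of whom 20 complete**

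| Replaced patients kept as failures | Result | One-sided p against 0.60 |
|---|---|---|
| 0 | 20/24 = 83.3% | 0.013 |
| 1 | 20/25 = 80.0% | 0.029 |
| 2 | 20/26 = 76.9% | 0.056 |
| 3 | 20/27 = 74.1% | 0.095 |

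One such patient moves p above 0.025.

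**5. Chance of a false pass**

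Let d be the share of enrolled patients lost before the first fraction (assumed). If true completion among enrolled patients is 0.60, completion among starters is q = 0.60 / (1 − d). The chance of passing is P(X ≥ 20 | 24, q).

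| d | q | Chance of passing |
|---|---|---|
| 0 | 0.600 | 1.3% |
| 5% | 0.632 | 2.8% |
| 10% | 0.667 | 5.9% |
| 15% | 0.706 | 12.3% |

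**6. Power if every enrolled patient counts**

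At n = 27 the exact cut-off is 22 (tail 0.0155 at 0.60). If the 90% target applies to all enrolled patients, power is 0.953. If it applies only to those who start PULSAR, the enrolled rate is 0.90 × (1 − d):

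- d = 5%: rate 0.855, power 0.81
- d = 10%: rate 0.81, power 0.59

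**The case against.** The strongest reply is that exclusion is never stated. Section 4.13 speaks of recruiting additional subjects, not of the analysis, and 2.3.1 read literally keeps a replaced patient as an enrolled non-completer, in which case there is no bias. This stands, and it is why the bias is put here as conditional. It does not settle the matter, because 9.3 omits enrolled and gives such a patient no clock.

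A second reply is that completion among PULSAR starters is a coherent endpoint, since the primary objective concerns cystectomy after the combination and the clock starts at PULSAR. That is fair as a design choice, but it is not what 2.3.1 says; choosing it would mean rewording 2.3.1 and reporting the earlier losses.

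Three stronger readings are tempting, and the documents do not support them:

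- **That the inhibitor lead-in is a run-in.** None is designed. Sections 3.1.7 and 4.8 also admit patients one to three weeks after starting the inhibitor. For them, much of any selection precedes enrolment, and 4.13 does not touch it. The table in 5.4 schedules no imaging between screening and the end of PULSAR, so progression in the gap would have to be found clinically.
- **That the 10% allowance covers the same loss as 4.13 a second time.** The 10% is a general drop-out rate and may refer to later withdrawals.
- **That counting drop-outs as failures caps completion at 24/27 = 88.9% and so defeats the 90% target.** The 90% is the design alternative, not a threshold to be reached.

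**Conclusion.** The conflict over the primary denominator is in the text and needs no assumption. The upward bias is conditional on two things: that replaced patients are left out of the analysis, and that some patients are lost before the first fraction. If either is absent, the bias is zero. A reader might infer that feasibility will certainly be overstated; the documents do not show that, because they give neither an exclusion rule nor a loss rate.

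Where both conditions hold, the decision can turn on very few patients: one under the exact test, three in the example under the 9.3 rule. With true completion of 60% among enrolled patients, an assumed early loss of 10% takes the chance of a false pass from 1.3% to 5.9%, beyond the one-sided 0.025. The denominator should be fixed before any outcome data are reviewed.

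**What to change.** - **2.3.1 and 9.3:** state that all registered patients form the primary denominator and that anyone who does not receive a first fraction is a non-completer.
- **4.13:** state that replacement adds a patient and does not remove the replaced patient from the primary analysis.
- **9.3:** report completion among PULSAR-treated patients as a supportive result, with the number of losses before PULSAR and their reasons.
- **9.2:** say whether the 10% drop-outs count as failures, and whether the 90% target refers to enrolled patients or to PULSAR starters; restate power to match.

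The change is to wording and needs no new procedures. It has two costs. The reported completion rate may be lower. The stated 91% power is secure only if the 90% target refers to all enrolled patients; if it refers to starters, power at n = 27 falls to about 0.81 or 0.59 for early losses of 5% or 10%, and the sample size or the target would have to be justified again.
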